This trial initially proposed to have 15 eligible stakeholders provide feedback about EMPOWER to inform improvements; to enroll 10 initial open trial cases and then to randomize 60 surrogate decision-makers of terminally, critically ill patients who are incapacitated or at risk of becoming incapacitated to EMPOWER or enhanced usual care. Beginning in April 2020, however, to meet the needs of family members in the COVID-19 pandemic, as well as to accommodate recruitment of human subjects with necessary social distancing practices, the RCT phase was paused to enter a new open trial phase (referred to hereafter as the COVID-19 open trial) that did not include randomization or a control arm. Upon approval of amendment #1610017622-13, we will return to the RCT phase. To adhere to recruitment strategies that were originally proposed, the number of participants enrolled in this study will not exceed the 60 participants initially projected, although due to the COVID-19 open trial, over 30 participants total may receive the EMPOWER intervention. Assessments will occur pre-intervention, immediately post-intervention, and then 1 month and 3 months from post-intervention assessment. Results will be used to seek NIH R01 funding for a larger-scale randomized controlled trial (RCT) intervention efficacy study of EMPOWER.

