1.1 Overview

To obtain stakeholder input on EMPOWER and refine the intervention manual, we propose to enroll up to 10 bereaved caregivers of patients who were incapacitated and treated in the ICU and 10 clinicians with expertise in ICU and/ or mental health care to have them review the study protocol and intervention manual and to obtain structured feedback on EMPOWER. Interviews will be audio-recorded, transcribed verbatim by trained staff, and kept confidential. Participants will also have the option to respond to interview questions through written response. In addition, we will enroll family caregivers and ICU patients to pilot the EMPOWER intervention and examine its effects on both informal caregivers and patients in the ICUs at New York Presbyterian Hospital (NYPH)- Weill Cornell, New York Presbyterian Hospital-Queens, and Memorial Sloan Kettering Cancer Center (MSK), as well as among surrogate decision-makers from outside hospitals recruited online. Surrogate decision-makers will be screened for emotional dependency on the patient and feelings of emotional distress related to the patients' ICU admission. Eligible surrogate decision-makers will be enrolled. The first 10 surrogate decision-makers will be enrolled in an open trial. A pilot RCT will then begin, randomizing surrogate decision-makers to receive either EMPOWER or enhanced usual care using a block-randomization strategy to determine condition assignment., A second open trial phase, only assigning surrogates to the EMPOWER trial in response to the COVID-19 pandemic, began on April 2020, with a return to the RCT following approval of amendment #1610017622-13. 60 surrogate decision makers will be enrolled in the RCT and COVID-19 open trial phases combined. Surrogate decision-makers will be assessed at 4 time points (T1 = baseline, T2 = up to one week following intervention, T3 = one month from T2, and T4 = three months from T2). The EMPOWER intervention will be administered by trained interventionists either in-person or via telehealth. The intervention sessions will be audio-recorded for training purposes. If participants agree, the sessions will be video-recorded. Patients' medical chart information will be abstracted

following the death of the patient. If the patient is not deceased by the end of their surrogate decision-maker's participation in the study, medical chart information will be abstracted at T4.

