2.0 Objectives

Specific Aim #1:

Develop EMPOWER for surrogate decision-makers of critically ill ICU patients who are at risk of becoming incapacitated and/or who are currently unable to make medical decisions.

There are no hypotheses for this objective. Stakeholders, including bereaved ICU patient caregivers and clinicians, will be asked to evaluate the EMPOWER intervention manual to increase its potential tolerability, acceptability, and efficacy. Data from the open trial of 10 surrogate decision-makers will also identify tactical and measurement issues involved in the delivery and outcome measurements used in EMPOWER.

Specific Aim #2:

Determine feasibility, tolerability, acceptability, and preliminary effects of EMPOWER on surrogate decision-maker mental health.

Hypothesis #2:

Revised EMPOWER will be feasible, tolerable, acceptable. Those who are randomized to EMPOWER will have reduced peritraumatic distress at post-intervention assessment (T2). Those who are randomized to EMPOWER will have reduced symptoms of PTSD, prolonged grief disorder, anxiety, and depression, and less decisional regret and experiential avoidance at one-month and three-month follow up from baseline (T3 and T4).

Specific Aim #3:

Examine the effects of EMPOWER on patient outcomes, including intensity of care and quality of life/quality of

death, in the months following baseline assessment.

Hypothesis #3:

Patients whose surrogate decision-makers receive EMPOWER will have better quality of death (for patients who died), better quality of life (for patients who are still alive) and more value-concordant care compared to those whose surrogate decision-makers receive enhanced usual care at one-month (T3) and three-month (T4) follow up from post-intervention assessment.

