5.1 Study Design and Methods

5.2 Study Design

There are two phases in this study. The manual refinement phase involves obtaining feedback from stakeholders (bereaved caregivers and clinicians) about the EMPOWER intervention manual using qualitative analysis followed by a modified Delphi method. The second phase involves piloting EMPOWER to obtain information on its feasibility, tolerability, acceptability, and preliminary effect size estimates in order to plan a larger, efficacy RCT. We will conduct an open trial of the intervention followed by a parallel-arm RCT comparing EMPOWER to enhanced usual care. In order to supplement RCT recruitment, adapt to restrictions in ICU visitation and meet the needs of family caregivers impacted by the COVID-19 pandemic, a secondary open trial occurred beginning April 2020, with a return to RCT procedures following approval of amendment #1610017622-13.

Manual Refinement:

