participant experiences and circumstances in the ICU, parts of the intervention may be omitted or amended at the discretion of the interventionist to meet the needs of the participant. The EMPOWER intervention is designed to be administered in the ICU, but to accommodate the varying needs of participants, may be administered in other private clinical settings on the campuses of the recruiting sites as well as via applications used for telehealth, such as but not limited to Webex or Zoom.

All participants who receive EMPOWER (both open trial and RCT cases) will be audio- and/or video-recorded for supervision and training purposes, with the participant's approval. They can opt out of video-recording and still participate, but audio-recording is mandatory.

EMPOWER is based on well-established cognitive-behavioral and acceptance-based techniques that aim to reduce maladaptive avoidance of distressing emotions. The EMPOWER interventionist will be compassionate and will attempt to provide validation of the surrogate decision-makers' experience; to teach tools for remaining present-focused; to explore the surrogate decision-maker's and the patient's wishes, values, and decision challenges; to increase their sense of acceptance and permission to experience challenging emotions; and to prepare them to cope with future distressing situations.

The primary outcome will be peritraumatic distress. We hypothesize that at post-intervention assessment, surrogate decision-makers who receive EMPOWER will have significantly lower symptoms of peritraumatic distress when compared to surrogate decision-makers who receive ICU enhanced usual care.

Secondary surrogate decision-maker outcomes will be surrogate decision-maker Prolonged Grief Disorder (PGD) symptom severity (either pre-loss/anticipatory or post-loss/bereavement grief) and experiential avoidance at one-month and three-month follow up. Exploratory surrogate decision-maker outcomes will be symptom severity of PTSD, depression, anxiety, and decision regret at one-month and three-month follow up. For both secondary and exploratory outcomes, we hypothesize that surrogate decision-makers who receive EMPOWER will have significantly lower symptoms compared to surrogate decision-makers who receive ICU enhanced usual care.

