5.1 Measures Used

Measures may be completed using hard copies, online (REDCap), or by RA interview, depending on the respondent's preference and research restrictions due to COVID-19. During the COVID-19 open trial, any hard copies will be mailed, digital copies will be emailed and RA interviews will occur over the phone or other telehealth medium.

Sociodemographic Characteristics:

Demographics: Surrogate decision-makers' will be asked in a self-report assessment occurring either in clinic or over the telephone their own and the patient's age (years), gender, race, education, mental health history, income, marital status, religious/spiritual beliefs, ACP knowledge/understanding, treatment preferences, prognostic understanding, and relationship with patient. Stakeholders will report on their own demographics.

Medical factors for Patients:

Patients' diagnoses (e.g., Stage IV pancreatic or NSCL cancer), reason for hospital/ICU admission, DNR/DNI order status, ACP items (including palliative care consultations), care plans obtained from the medical chart or ICU physicians and fellows, as well as clinically relevant symptoms related to patient incapacity, such as but not limited to, delirium. This information will be compiled as a medical chart abstraction and matched with surrogate-assessed patient treatment preferences assessed at T1 to create a measure of rates of value-concordant care. These medical factors, in addition to the CEQUEL ²³, will serve to measure the outcomes specified in Aim #3.

Psychosocial factors for Surrogate decision-makers:

Screener: Consists of items from 4 items from McGill Quality of Life¹⁹, two items from the Partner Dependency Scale ¹⁸, and two items from the Columbia Suicide Severity Rating Scale ²⁰.

Adult Surrogate Pre-intervention/ Baseline Assessment (T1): Psychiatric History, Demographics, and Treatment Preferences; Prolonged Grief Disorder (PG-12) Caregiver Version; ²⁴ ^{25,26}; Fear of Losing Loved Ones Scale (FOLLOS); Peritraumatic Distress Inventory (PDI) ²⁷; Peritraumatic Dissociative Experiences Questionnaire (PDEQ) ICU Version²⁸; Impact of ICU Events Scale-Revised (IES-R) ²⁹; Brief Experiential Avoidance Questionnaire (BEAQ); ³⁰State Trait Anxiety Inventory - State scale (STAI) ³¹; Patient Health

Questionnaire (PHQ-9); ³² Distress Tolerance Scale (DTS) ³³ revised version; Caregiver Self-Efficacy in the ICU Scale; Decision Regret Scale (DRS) – EMPOWER³⁴; Regret Assessment.

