Adult Surrogate Post-intervention Assessment (T2): PG-12 (if patient is alive); FOLLOS (if patient is alive); PG-13 (if patient is deceased); ²⁴ ^{25,26} PDI; PDEQ; IES-R; BEAQ; STAI; DTS revised version; Caregiver Self-Efficacy in the ICU Scale; DRS - EMPOWER; Regret Assessment; Post-Intervention Satisfaction Questionnaire (PISQ).

Adult Surrogate 1 Month Post-T2 Assessment (T3): PG-12 (if patient is alive); FOLLOS (if patient is alive); PG-13 (if patient is deceased); PDI; IES-R; BEAQ; STAI; PHQ-9; DTS revised version; Critical Care Family Satisfaction Survey- EMPOWER; CEQUEL-R (if patient is alive); CEQUEL ²³ (if patient is deceased); Quality of Life (if patient is alive); Quality of Death (if patient is deceased); DRS - EMPOWER; Regret Assessment; Medical Information Update

Adult Surrogate 3 Months Post-T2 Assessment (T4): PG-12 (if patient is alive); FOLLOS (if patient is alive); PG-13 (if patient is deceased); PDI; IES-R; BEAQ; STAI; PHQ-9; DTS revised version; CEQUEL-R (if patient is alive); CEQUEL (if patient is now deceased, but was alive at T3); Quality of Life (if patient is alive); Quality of Death (if patient is deceased); DRS - EMPOWER; Regret Assessment; Medical Information Update; Qualitative Exit Interview for (participants receiving EMPOWER intervention only).

Pediatric Surrogate Assessments: STAI, PDI, PG-12, IES-R, DRS-EMPOWER at all 4 timepoints, with brief demographics at T1, Post-Intervention Satisfaction Questionnaire at T2, and Qualitative Exit Interview at T4 (for participants receiving EMPOWER intervention only).

Measure Title	Time Points Used*	Description of Measure
McGill Quality of Life Scale	Screener	Items 5 through 8 are used to measure anxiety/depression.
Partner Dependency Scale (PDS)	Screener	Items 1 and 2 of the PDS are used to measure dependency. The language is altered to refer to the patient rather than a spouse.
Columbia Suicide Severity Rating Scale	Screener	Items 1 and 2 of the CSSRS are used to measure suicidal ideation.
Peritraumatic Distress Inventory (PDI) ICU Version	T1, T2, T3, T4	Measures peritraumatic distress.
Peritraumatic Dissociative Experiences Questionnaire (PDEQ) ICU Version	T1, T2	Measures experiences of dissociation that may occur in the ICU. Instructions are changed to prompt the participant to specifically answer the survey in reference to their experience in the ICU.
Impact of ICU Events Scale- Revised (IES-R)	T1, T2, T3, T4	Measures symptoms of PTSD.

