We will compute descriptive statistics to characterize the feasibility and acceptability of EMPOWER by examining helpfulness/satisfaction ratings, rates of recruitment, reasons for refusal, and number of modules/booster calls completed. Targets will include completion of 4/6 modules for feasibility and tolerability. Target acceptability will be an average score greater than 3 on the acceptability items in the post-intervention satisfaction questionnaire among participants who received EMPOWER. Tolerability will also be measured by open ended-responses to qualitative questions asked at T4 regarding negative experiences, emotional difficulties, and perceived costs and benefits of participating in the intervention. Drop-out will not be considered as a metric of tolerability due to the highly stressful and variable circumstances of ICU caregiving, unless participants drop out of the study and specifically express that they consider it to be too distressing. Qualitative data analysis will be used to analyze data from open-ended questions to identify the most helpful components of EMPOWER.

To evaluate the preliminary effects of EMPOWER among participants in the combined RCT and COVID-19 open trial phases, we will use a hierarchical linear modeling (HLM) and an intent-to-treat approach. HLM is statistically appropriate because of the clustering within interventionists and within surrogate decision-makers. HLM will correct for this clustering by modeling interventionists and surrogate decision-makers as random effects, as has been done in prior trials ^{38 39}. This will also provide a treatment assignment model coefficient and effect size estimate for our future, larger study.

HLM modeling will determine differences between surrogate decision-makers and patients assigned to EMPOWER vs. enhanced usual care. The primary outcome is post-intervention (T2) differences in PDI scores. Secondary outcomes are differences in scores on the PGD 12/13 and BEAQ at one-month (T3) and three-month (T4) follow up from T2. Exploratory outcomes are differences in scores on the IES-R, STAI, PHQ-9 and Decision Regret Scale at one-month (T3) and three-month (T4) follow up. HLM models will include covariates, either as fixed-effect or time-varying, if those variables are found to be significantly statistically associated with both intervention assignment and the outcome examined.

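### The EMPOWER-versus-usual-care comparison pools never-randomised COVID-19 open-trial participants with the RCT, calls this intent-to-treat, and specifies no randomised-only estimate

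*Combined protocol and SAP*

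**What the plan says.** All references are to the combined protocol and SAP.

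- **Analysis set.** Section 6.1, Data Analysis Plan, Specific Aim #2, evaluates preliminary effects "among participants in the combined RCT and COVID-19 open trial phases, we will use a hierarchical linear modeling (HLM) and an intent-to-treat approach". The resulting coefficient is to serve as the effect size for the larger study. The primary outcome is the T2 difference in PDI.
- **Open trial.** Section 1.1, Introduction, describes a phase "that did not include randomization or a control arm". Section 1.1, Overview, describes it as "only assigning surrogates to the EMPOWER trial in response to the COVID-19 pandemic".
- **Hypothesis.** Section 2.0, Hypothesis #2, is about randomised people: "Those who are randomized to EMPOWER will have reduced peritraumatic distress at post-intervention assessment (T2"). Section 5.2, Study Design, words the primary hypothesis by receipt: "surrogate decision-makers who receive EMPOWER will have significantly lower symptoms of peritraumatic distress".
- **Sample size.** Section 6.1, Statistical power and sample size considerations, counts open-trial participants in the total of 60 and projects 40 EMPOWER to 20 EUC. It states that d = 0.75 is still detectable with 80% power at alpha 0.05.
- **Covariates.** The Data Analysis Plan admits a covariate only if it is significantly associated with both assignment and outcome. Phase is not named, and the handling of T1 PDI is not stated.

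**The concern.** Intent-to-treat means analysing people in the arm to which they were randomised. Open-trial participants had no such allocation, so the label does not describe the planned comparison, and that comparison is not the one Hypothesis #2 states.

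The open trial adds people to the EMPOWER arm only. Anything that makes its participants' T2 PDI differ for reasons other than EMPOWER therefore passes into the treatment coefficient, in either direction. Such differences are plausible. Section 5.2 gives the reasons for the open trial as "In order to supplement RCT recruitment, adapt to restrictions in ICU visitation", among others. Section 5.1, Measures Used, makes its assessment remote: paper forms were mailed, digital forms emailed, and "RA interviews will occur over the phone or other telehealth medium".

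What is at stake is the effect size carried to the larger trial, and the reading of any significant pooled result. Conclusions on feasibility, tolerability and acceptability are not affected.

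**Working it through.** **Inputs from the documents:** N = 60 over both phases; projected 40 EMPOWER to 20 EUC; original RCT plan 30:30; d = 0.75; alpha 0.05; power 80%.

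**Assumptions:** two-sided test; 1:1 randomisation (inferred from 30:30); SD 1; T1–T2 correlation 0.6; phase shifts of 0.3 and 0.5 SD; no dropout; no interventionist effect.

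**1. The plan's own figure.** For 40:20 the standard error is √(1/40 + 1/20) = 0.274. Power is Φ(0.75/0.274 − 1.96) = 78.2% by normal approximation and 76.8% by t-test, with detectable d of 0.77 and 0.78. The stated 80% is approximately reproduced and slightly optimistic. For 30:30 the power is 82.8% and 81.5%.

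**2. Implied split.** Twenty EUC participants under 1:1 randomisation imply 20 randomised to EMPOWER, leaving 60 − 40 = 20 from the open trial. The non-randomised share of the EMPOWER arm is 20/40 = 0.5. With 10 to 30 open-trial participants, the share would run from 10/35 = 0.29 to 30/45 = 0.67.

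**3. Bias.** With a phase shift x, the EMPOWER mean moves by 0.5x and the EUC mean does not move. Unadjusted bias is 0.5 × 0.3 = 0.15 SD or 0.5 × 0.5 = 0.25 SD.

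**4. Error rate with no true effect** (simulation, 6,000 trials per setting, 20 + 20 + 20; values for shifts 0.3 / 0.5):

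| Pooled model | Bias (SD) | Two-sided error |
|---|---|---|
| No T1 adjustment | 0.15 / 0.25 | 8% / 14% |
| T1 covariate, same shift at T1 and T2 | 0.06 / 0.10 | 6% / 7% |
| Change from T1, same shift at both | 0 / 0 | 5% / 5% |
| T1 covariate, shift at T2 only | 0.15 / 0.25 | 9% / 17% |
| Change from T1, shift at T2 only | 0.15 / 0.25 | 8% / 15% |

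The randomised-only comparison has bias near 0 and error of about 5%.

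**5. The covariate rule, if phase is offered to it** (5% level, no T1). The plan does not say how the association is tested.
- Phase tested alone: it enters 19% / 44% of the time, bias is 0.09 / 0.09 SD and error about 6%.
- Phase tested given assignment: it enters 16% / 35% of the time, bias is 0.09 / 0.11 SD and error 9% / 12%.

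**6. Overall accuracy (root mean squared error, RMSE; shifts 0.3 / 0.5).**

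| Setting | Pooled | Randomised-only |
|---|---|---|
| Unadjusted | 0.31 / 0.37 | 0.32 / 0.32 |
| T1 covariate, same shift at T1 and T2 | 0.23 / 0.24 | 0.26 / 0.26 |
| T1 covariate, shift at T2 only | 0.26 / 0.33 | 0.26 / 0.25 |

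Unadjusted, pooling becomes the less accurate choice above x = √[(1/20 + 1/20) − (1/40 + 1/20)] / 0.5 = √0.025 / 0.5 = 0.32 SD. With T1 adjusted and a T2-only shift the threshold is 0.316 × √(1 − 0.36) = 0.25 SD.

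**7. Randomised-only power.** At 20:20 the unadjusted t-test has 64% power at d = 0.75, with detectable d of 0.91 at 80% power. With 10 or 30 open-trial participants, power would be 74% or 51%.

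**The case against.** The pooling is disclosed, and it was a pandemic adaptation of a proof-of-concept pilot. The RCT ran before and after the open trial. Adult criteria 1, 3, 4 and 5 match, and remote delivery and assessment are also allowed in the RCT. Intent-to-treat might be meant loosely, as analysis by assigned condition.

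The model has surrogate random effects, which suggests repeated measures. If T1 PDI is among them, a shift present at both times largely cancels, so 8% and 14% need not be the expected error. Phase is tied to assignment by construction, so the covariate rule depends only on the outcome test and admits phase more often as the shift grows. Tested alone, that rule has RMSE of about 0.29 and 0.30 at shifts of 0.3 and 0.5, slightly better than the randomised-only 0.32. On this view, a randomised-only sensitivity analysis with a corrected label would be enough.

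Much of this stands. Pooling is not always less accurate, and the size of the problem depends on an unknown shift. But the plan does not say that T1 enters the model, and no baseline adjustment removes a shift arising only at T2. With phase tested given assignment, the rule's RMSE is 0.35 at a shift of 0.5, against about 0.31 randomised-only. A model with a phase term can separate phase from treatment, but only by discarding the open trial's contribution to the contrast. Disclosure does not make the comparison randomised. Since Hypothesis #2 concerns randomised people, the estimate that answers it belongs in the primary position.

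**Conclusion.** The concern holds. The intent-to-treat label is wrong as written, the planned analysis does not match Hypothesis #2, and no analysis that would isolate the randomised comparison is specified. This follows from the text alone.

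The consequence is partial confounding: the RCT phases contain both arms and only the open-trial portion lacks concurrent controls. Its size is conditional. Under the inferred 20 + 20 + 20 split, bias is half of any phase shift that the model does not adjust away. It ranges from near zero (same shift at both times, change from baseline) to 0.15–0.25 SD (unadjusted, or a T2-only shift) for assumed shifts of 0.3–0.5 SD. Against a design effect of 0.75, a bias of 0.25 SD is one third. The direction is unknown. The interventionist random effect is not in these figures, so the power and interval widths are approximate for the planned model. The point should be fixed before analysis.

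**What to change.** In section 6.1, Data Analysis Plan:

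- Make the primary EMPOWER-versus-EUC comparison, for T2 PDI and the T3/T4 outcomes, all randomised participants from before the pause and after resumption, analysed as randomised. Use T1 PDI as a covariate for T2 PDI.
- Take the effect size for the larger trial from this comparison.
- Use open-trial data for feasibility, tolerability, acceptability and within-group change.
- Report the pooled comparison, adjusted for the T1 value, as supportive and labelled non-randomised.
- Do not present a pooled model with a phase term as separate evidence. Its treatment coefficient equals the randomised-only difference, or nearly so once T1 is adjusted.
- Align the wording of the primary hypothesis in section 5.2 with Hypothesis #2.

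In the sample size section, restate power and detectable effect for the actual randomised counts.

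No new data are needed. T1 PDI is in the adult baseline battery, and paediatric surrogates complete "STAI, PDI, PG-12, IES-R, DRS-EMPOWER at all 4 timepoints". The cost is wording, one model on a subset, and precision:

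| | Randomised-only (20:20) | Pooled (40:20) |
|---|---|---|
| 95% half-width, unadjusted | 0.64 SD | 0.55 SD |
| 95% half-width, T1 adjusted | 0.52 SD | 0.44 SD |
| Power at d = 0.75, unadjusted | 64% | 77% |
| Power at d = 0.75, T1 adjusted | 81% | 91% |

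The power rows assume no phase shift, and the T1-adjusted rows assume a correlation of 0.6. Under that correlation, adjusting for T1 recovers most of what restricting to randomised participants loses.

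### The PDI model states no visit, arm-by-visit or baseline terms, so the treatment assignment coefficient is not tied to the primary T2 difference

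*Combined protocol and SAP*

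**What the plan says.** The target is clear. Section 5.2 (Study Design) states: "We hypothesize that at post-intervention assessment, surrogate decision-makers who receive EMPOWER will have significantly lower symptoms of peritraumatic distress". Section 6.1 (Data Analysis Plan, Specific Aim #2) repeats it: "The primary outcome is post-intervention (T2) differences in PDI scores".

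The model is described only in part. For the combined RCT and COVID-19 open trial phases, section 6.1 says "we will use a hierarchical linear modeling (HLM) and an intent-to-treat approach", and adds: "HLM will correct for this clustering by modeling interventionists and surrogate decision-makers as random effects". The model quantity it names is in this sentence: "This will also provide a treatment assignment model coefficient and effect size estimate for our future, larger study". On other fixed terms it says only: "HLM models will include covariates, either as fixed-effect or time-varying, if those variables are found to be significantly statistically associated". The association must be with both assignment and outcome.

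The table in section 5.1 (Measures Used) gives the PDI schedule: "Peritraumatic Distress Inventory (PDI) ICU Version T1, T2, T3, T4".

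Section 6.1 does not say which visits enter the PDI model, whether visit and arm-by-visit are fixed effects, how T1 PDI is used, or which coefficient or contrast is the T2 estimate.

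**The concern.** A surrogate random effect can be separated from residual error only if a surrogate contributes more than one record. The text therefore implies a repeated-measures model of PDI. In such a model the meaning of the assignment coefficient depends on the fixed terms. If arm is a main effect only, the coefficient is the arm difference averaged over the modelled visits. If arm-by-visit terms are present, it is the difference at the reference visit, which could be T2 or T1.

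An analyst following section 6.1 could report any of these as the primary result and could choose after seeing the data. The same number is meant to inform the size of the next trial, so the ambiguity would carry forward.

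**Working it through.** **Inputs from the documents.** Section 6.1 (Statistical power and sample size considerations): d = 0.75, alpha 0.05, about 80% power, 30:30 as first planned and 40:20 as projected. PDI visits are T1–T4 (section 5.1).

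**Assumptions, because the documents give no figures.** Two-sided test, unit variance at every visit, equal correlation rho between visits, complete data, no interventionist clustering, and a true T1 difference of zero. The effect courses are also assumed.

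**Step 1: the plan's own power.** For two means at one time point, the noncentrality is d × √(n1·n2/(n1+n2)).
- 30:30: 0.75 × √15 = 2.905. Power is 81.5% (t) or 82.8% (normal).
- 40:20: 0.75 × √13.33 = 2.739. Power is 76.8% (t) or 78.2% (normal).

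The stated figure of about 80% thus reproduces as a single-time-point comparison. This does not settle which model coefficient is meant.

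**Step 2: what the coefficient estimates.** A random-intercept model was fitted to one simulated data set of 3,000 subjects. True effects were 0 at T1, −0.75 at T2 and −0.375 at T3 and T4.

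| Fixed terms | Arm coefficient (SE) | True target |
|---|---|---|
| arm + visit, T1–T4 | −0.32 (0.03) | −0.375, average |
| arm + visit, T2–T4 | −0.45 (0.03) | −0.50, average |
| arm × visit, T2 reference | −0.70 (0.04) | −0.75, T2 difference |
| arm × visit, T1 reference | 0.06 (0.04) | 0, baseline difference |

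Each estimate lies within two standard errors of its target. The same random-effect structure gives three kinds of estimand: an average, the T2 difference or the baseline difference.

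**Step 3: power of an averaged coefficient at 40:20.** Over k visits it estimates the mean of the k visit effects. The SD of a subject mean is √((1+(k−1)rho)/k).
- k = 4: SD is √(2.2/4) = 0.742 at rho 0.4 and √(3.1/4) = 0.880 at rho 0.7.
- k = 3: SD is √(1.8/3) = 0.775 at rho 0.4 and √(2.4/3) = 0.894 at rho 0.7.

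Example, effect at T2 only, T1–T4 rows, rho 0.4: the estimate is 0.75/4 = 0.1875, standardised 0.1875/0.742 = 0.253, noncentrality 0.253 × 3.651 = 0.92, power 15%.

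The T2 contrast has 76.8% power in the first three rows below, where the true T2 effect is 0.75. Ranges run over rho 0.4–0.7.

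| True effect at T2, T3, T4 | T1–T4: estimate, power | T2–T4: estimate, power |
|---|---|---|
| 0.75, 0, 0 | 0.19, 12–15% | 0.25, 17–21% |
| 0.75, 0.375, 0.19 | 0.33, 27–36% | 0.44, 42–53% |
| 0.75, 0.75, 0.75 | 0.56, 63–78% | 0.75, 85–94% |
| 0, 0.5, 0.5 | 0.25, 18–23% | 0.33, 27–34% |

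In the last row there is no T2 effect, so each rejection would wrongly be read as support for the T2 hypothesis.

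**Step 4: value of adjusting for T1 PDI.** The residual SD at T2 becomes √(1−rho²): 0.954 at rho 0.3 and 0.714 at rho 0.7. With similar T1 means in the two arms, the T2 contrast at 40:20 rises from 76.8% to 81% (rho 0.3) and 96% (rho 0.7).

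**The case against.** The plan ties the primary comparison to T2 in three places: Hypothesis #2 in section 2.0, section 5.2 and section 6.1. It also names T3 and T4 separately for the other outcomes, which one all-visit coefficient could not deliver. The coefficient sentence says the model will *also* provide it, so it need not be the only effect estimated. An arm-by-visit model with T2 as reference fits the wording and gives the right answer. This is a proof-of-concept pilot. Booster sessions at 2 and 4 weeks might sustain the effect, and then averaging over T2–T4 is undiluted and more powerful. The lowest power figures need an effect confined to T2 with T1 as an outcome row, and the documents state neither.

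All of this stands. A reader might infer that the plan tests one arm difference averaged over all visits and leaves T2 untested. The documents do not support that, because they specify no such model and silence on visit terms does not exclude them.

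A reader might also infer that randomisation makes the T1 difference zero. That does not hold for the analysed set, which includes the COVID-19 open trial, described in section 1.1 as having neither randomisation nor a control arm. If the RCT part is 1:1, a 40:20 split leaves about 40 − 20 = 20 EMPOWER participants non-randomised. A real T1 difference would enter a four-visit average with weight 1/4.

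What the objection does not answer is that naming T2 states the aim but not the model that reaches it.

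**Conclusion.** The concern holds as under-specification of the primary analysis, not as proof that the wrong hypothesis is tested. The fixed part of the PDI model is not stated, so it cannot be confirmed that the reported coefficient estimates the T2 difference.

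If the literal main-effect reading were used, power could fall from about 77% to between 12% and 53% for a T2-only or fading effect, depending on the course and the rows used. For a fully persistent effect over T2–T4 it would rise to 85–94%. These figures rest on the assumed courses, equal correlations of 0.4–0.7, complete data, no T1 difference and no interventionist clustering. The ambiguity itself rests on none of them. The point is worth settling before analysis, since the estimate also feeds the larger trial.

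**What to change.** In section 6.1, Specific Aim #2, replace the general reference to an assignment coefficient with a stated PDI model:
- T2, T3 and T4 as outcome visits, visit as a categorical factor, and arm-by-visit terms.
- T1 PDI as a prespecified covariate whatever its significance. The present rule would omit a strongly prognostic baseline score that was not significantly associated with arm.
- No constraint that the arms share a T1 mean, because the pooled set is partly non-randomised. Adjusting for T1 PDI does not remove other differences between the phases.
- The arm contrast at T2 as the primary test and as the effect size carried to the larger trial.

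Fit separate models of the same form, with T3 and T4 contrasts, for each secondary and exploratory outcome, using only the visits at which it is measured. PHQ-9, for example, has no T2 record. The PDI model cannot serve those outcomes.

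The cost is SAP wording and a few model terms, with no new data. The trade-off is less power than averaging if the effect is constant over T2–T4: 77% against 85–94% without baseline adjustment. Adjusting for T1 PDI offsets some of that.
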